6.5.2. Baseline NSAA Total score

The following endpoints will be evaluated by Baseline NSAA total score strata:

- Change from Baseline at Week 52 in the NSAA total score
- Change from Baseline at Week 52 in the 10 meter run/walk test velocity.
- Change from Baseline at Week 52 in the rise from floor velocity.
- Baseline NSAA total score strata will be defined by the observed median of baseline NSAA total score based on all participants in the FAS during the reporting period. The 2 subgroups will be determined as below:
 1. < Median
 2. ≥ Median

Analysis:

- Analysis set: FAS ([Section 4](#)).
- Analysis methodology:

For each baseline NSAA total score strata separately, change from baseline will be analyzed using an MMRM approach ([Section 5.2.1.1](#)) including fixed effects for treatment group (categorical variable), visit (ordered categorical variable), and treatment group by visit interaction with additional fixed effects for screening age covariate (continuous variable) and screening age by visit interaction.

For each baseline NSAA total score strata, estimates of the mean changes from Baseline, standard error of each LS mean, and 95% confidence intervals for fordadistrogene movaparvovec and placebo will be provided for each visit along with the mean treatment group difference and the corresponding standard error, two-sided p-value, and two-sided 95% confidence interval for the mean difference at each visit.

- Intercurrent events and missing data: All available data in the reporting period will be included. The intercurrent events and missing data will be handled as described in [Section 2.2.1](#) and [Section 2.2.2](#) accordingly.
- For each baseline NSAA total score strata separately, the summary for each endpoint will be performed the same way as described in the corresponding main analysis in [Section 6.1](#) and [Section 6.2](#).

6.5.3. Geographic Region

The following endpoints will be evaluated by geographic regions:

- Change from Baseline at Week 52 in the NSAA total score
- Change from Baseline at Week 52 in the 10 meter run/walk test velocity.
- Change from Baseline at Week 52 in the rise from floor velocity.

The geographic regions in this study will be categorized as North America, Europe, and Asia-Pacific.

Analysis:

- Analysis set: FAS ([Section 4](#)).
- Analysis methodology:

For each geographic region strata separately, change from baseline will be analyzed using an MMRM approach ([Section 5.2.1.1](#)) including fixed effects for treatment group (categorical variable), visit (ordered categorical variable), and treatment group by visit interaction with additional fixed effects for baseline (continuous variable) and baseline by visit interaction, with additional fixed effects for screening age covariate (continuous variable) and screening age by visit interaction

For each geographic region strata, estimates of the mean changes from Baseline, standard error of each LS mean, and 95% confidence intervals for fordadistrogene movaparvovec and placebo will be provided for each visit along with the mean treatment group difference and the corresponding standard error two-sided p-value, and two-sided 95% confidence interval for the mean difference at each visit.

- Intercurrent events and missing data: All available data in the reporting period will be included. The intercurrent events and missing data will be handled as described in [Section 2.2.1](#) and [Section 2.2.2](#) accordingly.
- For each geographic region strata separately, the summary for each endpoint will be performed the same way as described in the corresponding main analysis in [Section 6.1](#) and [Section 6.2](#). No plots will be produced for these analyses.

6.6. Baseline and Other Summaries and Analyses

6.6.1. Baseline Summaries

All summaries will be performed for the Safety Analysis Set population. Demographic and baseline characteristics will also be performed for the FAS populations.

1. Demographic characteristics will be summarized. Age categories to display are ≥ 4 to < 5 years, ≥ 5 to < 6 years, ≥ 6 to < 7 years, and ≥ 7 to < 8 years.

2. Screening age strata (< 6 years and ≥ 6 years old) will be summarized for fordadistrogene movaparvovec and placebo and for combined treatment groups using number and percent of participants.
3. Baseline physical measurements (including height and weight) will be summarized for fordadistrogene movaparvovec and placebo and for combined treatment groups.
4. The below will be summarized for fordadistrogene movaparvovec and placebo and for combined treatment groups using number and percent of participants:
 - DMD genetic results.
 - Enrollment geographical region and country.
5. Background glucocorticoid regimen will be summarized for fordadistrogene movaparvovec and placebo and for combined treatment groups. Prednisolone and prednisone will be combined for this analysis. The number and percent of participants for each glucocorticoid being received at Screening will be presented. Descriptive statistics (N, mean, SD, median, Q1, Q3, minimum and maximum) will be presented for
 - Daily dose (mg/kg) for each glucocorticoid the participant is receiving at Screening.
 - Duration of glucocorticoid use (months) for glucocorticoid dose the participant is receiving at Screening.
 - Age at initiation of any glucocorticoid use.
6. General medical history will be summarized for fordadistrogene movaparvovec and placebo and for combined treatment groups.
7. Prior medications will be summarized for fordadistrogene movaparvovec and placebo and for combined treatment groups.
8. Study inclusion and exclusion criteria at Screening will be summarized for screen failures. IP administration eligibility will be summarized by randomized treatment assignment (ie, fordadistrogene movaparvovec and placebo) for participants who were randomized but not treated.
9. The below will be summarized for fordadistrogene movaparvovec and placebo and for combined treatment groups using descriptive statistics (N, mean, SD, median, Q1, Q3, minimum, and maximum):
 - Baseline NSAA total score.
 - Screening age (years) covariate.
 - Age (years) at dosing with IP on Year 1 Day 1.

6.6.2. Study Conduct and Participant Disposition

1. The below participant populations/sets will be summarized for fordadistrogene movaparvovec and placebo and for combined treatment groups.
 - Enrolled.
 - Randomly assigned to investigational product.
 - Treated.
 - Full Analysis Set.
 - Safety Analysis Set (through Week 52).
 - Biceps Brachii Muscle Biopsies
 - Viral Vector Shedding Kinetics
2. Participant disposition (eg, discontinuation from study, reason for discontinuation, completed study, and ongoing) will be summarized for fordadistrogene movaparvovec and placebo.
3. Medication errors will be listed.
4. Important protocol deviations will be summarized.

6.6.3. Study Treatment Exposure

The actual administered dose of fordadistrogene movaparvovec in vg and vg/kg will be summarized (n, mean, SD, median, Q1, Q3, minimum and maximum) for Year 1 Day 1 in the Safety Analysis Set (through Week 52) (Section 4). The percent of planned volume of IP administered will be categorized as 0% to $\leq 25\%$, $>25\%$ to $\leq 50\%$, $>50\%$ to $\leq 75\%$, and $>75\%$ for fordadistrogene movaparvovec and placebo.

6.6.4. Concomitant Medications

The World Health Organization (WHO)-Drug coding dictionary will be used to classify concomitant medications.

The number and percent of participants who took each concomitant medication will be provided for fordadistrogene movaparvovec and placebo in the Safety Analysis Set (through Week 52) (Section 4).

6.7. Safety Summaries and Analyses

All analyses will be performed for the Safety Analysis Set (through Week 52).

6.7.1. Adverse Events

Incidence of TEAEs (all-causality and treatment-related) in the reporting period will be summarized by SOC, PT, and severity for fordadistrogene movaparvovec and placebo. Adverse events may be clustered to reflect medical concepts.

A summary of the TEAEs (all-causality and treatment-related) occurring during the reporting period will be tabulated by PT sorted by decreasing incidence for fordadistrogene movaparvovec and placebo. The most commonly reported TEAEs will be summarized using those PTs with high frequency (cutoff depends on the final frequency of TEAEs) for fordadistrogene movaparvovec-dosed participants in the safety analysis set.

Deaths and SAEs will be listed and incidence of SAEs(all causality and treatment-related) will be summarized by SOC and PT for fordadistrogene movaparvovec and placebo.

A summary of the SAEs (all-causality and treatment-related) occurring during the reporting period will be tabulated by PT sorted by decreasing incidence for fordadistrogene movaparvovec and placebo. The most commonly reported SAEs will be summarized using those PTs with high frequency (cutoff depends on the final frequency of serious TEAEs) for fordadistrogene movaparvovec-dosed participants in the safety analysis set.

For each participant who reported a TEAE (all-causality or onset treatment-related), the time (in days) to (date of onset of the event - date of dosing + 1) for that TEAE will be summarized by PT as continuous data. Participants with multiple TEAEs will be included multiple times in the summary statistics. Events that occur on the day of dosing will have a time of onset as day 1.

For each participant who reported a serious TEAE (all-causality or treatment-related), the time (in days) to onset (date of onset of the event - date of dosing + 1) for that serious TEAE will be summarized by PT as continuous data. Participants with multiple serious TEAEs will be included multiple times in the summary statistics. Events that occur on the day of dosing will have a time of onset as Day 1.

Adverse events of interest will be summarized using incidence of all-causality AEs (by severity) and SAEs (across all severities). Several PTs would be combined as cluster terms, and incidence for both component PTs and cluster terms will be included. Cluster categories and PTs with “Peri infusion” will include AEs of interest with an onset in the first 2 weeks after dosing (Day 1 through Day 14) while “Late Onset” will include AEs of interest with an onset date after week 4 (Week 5 or later). The final list of AEs of interest will be maintained in a separate document and finalized before the database release.

Onset of AEs of interest (all-causality) will be summarized by intervals. The interval is defined as the number of weeks rounded to next highest integer from the fordadistrogene movaparvovec or placebo administration to the earliest of date of AE of interest or date of data cut-off (i.e., [end date – dosing date +1]/7 for weeks. The total duration of follow up for each participant is relative to death/study discontinuation/or data cut-off. For example, week 1 is for days 1-7 and week 2 is for days 8-14).

For each duration of follow-up interval, total number of AEs of interest that occur during an interval will contribute to the numerator of the percentage. Total count of AEs of interest that occur in the entire reporting period will contribute to the denominator of the percentage. Day 390 or one day prior to Year 2 dosing will be considered as having follow-up up to 52 weeks.

The AEs of interest for both cluster terms and the component PTs will be summarized by interval durations in weeks. For these AEs of interest cluster terms and the components PTs, duration of the adverse events will be summarized descriptively (N, mean, SD, median, Q1, Q3, minimum, and maximum). Participants with multiple AEs of interest will be included multiple times in the summary statistics.

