2.3.2. Treatment Groups and Reporting Periods for Analysis

In the study schematic in Figure 1, the study period and treatment groups to be included in the primary analysis are encircled in red.

- Treatment groups:
 1. fordadistrogene movaparvovec – participants randomized to Cohort 1 to receive a single dose of fordadistrogene movaparvovec on Day 1 (Year 1 Day 1).
 2. Placebo – participants randomized to Cohort 2 to receive a single dose of placebo on Day 1 (Year 1 Day 1).

- Reporting Period:

All analyses will be relative to Day 1 (Year 1 Day 1) investigational product (IP) administration.

The reporting period will include all data from the day of the Year 1 Day 1 IP administration through Week 52. Specifically, all participant data from Day 1 to the earliest of (1) Day 390 (the upper limit of the Week 52 analysis visit window or (2) one day before the Year 2 Day 1 IP administration.

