5. GENERAL METHODOLOGY AND CONVENTIONS

The primary analysis will occur after at least 90 FAS participants complete Day 360 (Visit 19) or discontinued from the study prior to Week 52 if they had received Year 1 IP at least

one year prior to the data cutoff. There are 2 options for IAs, both of which are designed to provide data to support an earlier regulatory submission for BLA/MAA as described in [Section 7](#).

As a general rule, all efficacy analyses including the primary endpoint, secondary endpoints, and other endpoints will be conducted based on all FAS participants regardless of adherence to background or protocol mandated glucocorticoid regimens during the first 52 weeks after study drug infusion, unless specified otherwise.

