5.2.2. Analyses for Time-to-Event Endpoints

Time-to-event endpoints will be summarized using the Kaplan-Meier (K-M) method and estimated K-M curves will be displayed graphically. Graphs will describe the number of participants at risk over time. Censoring definitions are provided in [Section 3.3.4](#) under the specific time to event endpoints.

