No imputation for missing data will be performed for other analysis approaches.

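### Duration of adverse events of interest is summarised with plain descriptive statistics and no rule for events still ongoing, so the mean duration is understated whether those events are dropped or cut

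*SAP*

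**What the plan says.** Section 6.7.1 plans, by cluster term and component preferred term (PT), that "duration of the adverse events will be summarized descriptively (N, mean, SD, median, Q1, Q3, minimum, and maximum". The unit is the event: "Participants with multiple AEs of interest will be included multiple times in the summary statistics". Late-onset clusters "will include AEs of interest with an onset date after week 4 (Week 5 or later", so an event can begin at any time up to the end of observation.

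Observation is finite. Section 2.3.2 confines the reporting period to "all participant data from Day 1 to the earliest of (1) Day 390" or the day before Year 2 dosing. Section 6.7.1 names further ends of follow-up: "The total duration of follow up for each participant is relative to death/study discontinuation/or data cut-off". Section 5 adds that "The primary analysis will occur after at least 90 FAS participants complete Day 360 (Visit 19" or discontinue, subject to its one-year condition, while Section 2.3.1 plans 99. Some participants may therefore be cut earlier.

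No passage defines duration or its end date, or plans a count of ongoing events. The cut-off rule in Section 6.7.1 concerns the interval to onset. Section 5.3 closes with "No imputation for missing data will be performed for other analysis approaches". Section 5.2.2 states that "Time-to-event endpoints will be summarized using the Kaplan-Meier (K-M) method", and Section 3.3.4 gives the censoring rule for vector clearance. Neither is applied to AE duration.

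**The concern.** The duration of an event that has not resolved is right-censored: only a lower bound is known. A mean, SD and quartiles computed as if every duration were complete need some value for such events, or must leave them out. Leaving them out removes long events selectively. Counting them at the time observed treats a minimum as the full length. Late-onset events are most exposed because they may have little time left in which to resolve.

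The stake is descriptive but real. The treatment is a single infusion that cannot be withdrawn, and readers will look to this table for how long AEs of interest last. As written, two programmers could produce different tables, and neither would show how many events were still open.

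**Working it through.** The plan states no duration and no share of ongoing events, so there is no figure of its own to reproduce. The check asks for the direction of the bias, and its size under stated assumptions.

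**Inputs from the SAP.** Observation ends at Day 390 (Section 2.3.2). Peri-infusion onset is Days 1–14, and late onset is after Week 4, hence from Day 29 (Section 6.7.1).

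**Assumptions.** Onset is uniform within each range. Duration D is exponential with mean m. Nobody is cut before Day 390; earlier cuts would add censoring.

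**Formulas.** Let W = 390 − onset be the time left.
- Share ongoing: p = E[exp(−W/m)]
- Mean if ongoing events are cut: E[min(D, W)] = m(1 − p), so the relative shortfall equals p
- Mean if they are dropped: m − A/(1 − p), where A = E[W·exp(−W/m)]

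For late onset, W is uniform on 0 to 390 − 29 = 361, so p = (m/361)(1 − exp(−361/m)) and A = [m² − (m² + 361m)·exp(−361/m)]/361.

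**Worked case, late onset, m = 90.** exp(−361/90) = 0.0181. Then p = 0.2493 × 0.9819 = 0.245. Cut mean = 90 × 0.755 = 68. A = (8100 − 40590 × 0.0181)/361 = 20.4. Dropped mean = 90 − 20.4/0.755 = 63.

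**Results (days).** Means come from the formulas, with W uniform on 376–389 for peri-infusion events. Medians come from a simulation of 400,000 events per scenario, which also agreed with the means.

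| Onset | True mean / median | Ongoing | Mean if cut | Mean if dropped | Median, cut / dropped |
|---|---|---|---|---|---|
| Late | 30 / 21 | 8.3% | 27.5 (−8%) | 27.3 (−9%) | 19 / 19 |
| Late | 90 / 62 | 24% | 68 (−24%) | 63 (−30%) | 49 / 46 |
| Late | 180 / 125 | 43% | 102 (−43%) | 86 (−52%) | 80 / 67 |
| Peri-infusion | 30 / 21 | 0% | 30 (0%) | 30 (0%) | 21 / 21 |
| Peri-infusion | 90 / 62 | 1.4% | 89 (−1%) | 84 (−6%) | 62 / 61 |
| Peri-infusion | 180 / 125 | 12% | 158 (−12%) | 128 (−29%) | 125 / 105 |

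**Other shape.** With lognormal durations (sigma 1), late onset and a true mean of 90 days, 23.3% are ongoing. The mean is 65 if cut (65/90, −28%) and 59 if dropped (59/90, −34%).

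**Kaplan-Meier.** With ongoing events censored, the simulated median returns to 21, 62 and 125 days in both onset groups, and to 55 against a true 55 in the lognormal case.

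**The case against.** The strongest reply is that the SAP never says ongoing events are dropped or cut; that is inferred from silence. Section 3.5.1 makes an event treatment-emergent by its start. Follow-up runs for years (Section 2.3), and the analysis is set by a data cut-off. An event open at Day 390 could therefore have a later recorded end date that a programmer might use. This stands in part. It would reduce the censoring, but would not remove it at the data cut-off, and Section 2.3.2 points against using such dates. A reader should not infer that the plan prescribes dropping or cutting, only that either choice biases the mean down.

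A reader might also infer three stronger things that the document does not support.
- **The longest events would look the mildest.** They would not. In the late-onset rows the reported means still rise with the true mean (27, 63, 86 if dropped). Differences shrink, but the order holds.
- **Medians are always understated.** They are not. If every truncated duration already exceeds the median, cutting leaves it unchanged, as in the peri-infusion rows.
- **The arms are truncated unequally.** Section 4 does describe immediate withdrawal of some Cohort 2 participants with partial data, but gives no numbers from which a difference between arms could be derived.

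Two further objections hold. Duration is not among the safety endpoints in Section 2.2, which names incidence, severity and causal relationship. And ordinary Kaplan-Meier confidence intervals at event level would ignore repeated events in one participant; the fix allows for this.

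**Conclusion.** The point holds as a flaw in a descriptive safety table. Plain statistics are the wrong summary for durations that may be incomplete, and no rule elsewhere repairs it. The downward direction for the mean is certain for either handling within the reporting period. The size is not known from the SAP: the list of AEs of interest sits in a separate document and no durations are given. Under the stated assumptions the loss ranges from nothing, for peri-infusion events averaging 30 days or less, to about half, for late-onset events averaging 180 days whose open cases are dropped. The change is worth making before database release. It does not bear on the primary test or type I error.

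**What to change.** In Section 6.7.1:
1. Define duration and its end date, and say whether end dates recorded after the reporting period may be used.
2. Report the number and percent of events ongoing at end of follow-up, by arm, cluster and PT.
3. Give the Kaplan-Meier median and quartiles of duration, with ongoing events censored at the end of the reporting period, withdrawal, death or data cut-off, whichever applies.
4. Omit 95% confidence intervals, or base them on a participant-clustered method or on the first event per participant.
5. Keep the plain descriptive statistics only if they are labelled as covering resolved events only.

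The cost is SAP wording and added table columns. No new data are needed, and the method is already in Section 5.2.2. The drawback is that upper quartiles may not be reached in small clusters; the count of ongoing events then carries the information.

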6.7.2. Laboratory Data

Central and local laboratory test results will be combined for reporting purposes.

Incidence of laboratory test abnormalities will be summarized for fordadistrogene movaparvovec and placebo without regard to baseline abnormality, for normal baseline, and for abnormal baseline. If there is a local and central laboratory collection on the same day, both values will be considered for analysis.

For select laboratory test parameters, data will be summarized and displayed graphically as described below;

Parameter	Presentation		
	Table: Changes and % changes from baseline By visit	Shift table: <LLN, normal, >ULN By visit	Graph: Box-plot
GLDH	X	X ^a	X (observed values)
CK	X		X ^f
GGT	X	X ^b	X (observed values)
C3 and C4	X		X (observed values)
Platelets	X	X ^c	X (observed values)
Creatinine	X		X (observed values)
cTn-I	X ^d (observed values)	X ^e	X ^f (observed values)

- $\geq 2xULN$ and $< 3xULN$, $\geq 3xULN$ and $< 4xULN$, and $\geq 4xULN$ will be applied in shift table
- $>ULN$ -and $\leq 2.5 x ULN$, > 2.5 and $\leq 5.0 x ULN$, > 5.0 and $\leq 20.0 x ULN$, $> 20.0 x ULN$ will be applied in shift table
- ≥ 75 and $< LLN$, ≥ 50 and < 75 , ≥ 25 and < 50 , and < 25 and will be applied in shift table (in $10^3/mm^3$)
- The ratio $cTn-I/ULN$ will be used in the shift table

- e. cTn-I/ULN ratio ≥ 3 - <10 , ≥ 10 - <100 , ≥ 100
- f. Spaghetti plot of % change from baseline in CK and ratio cTn-I/ULN will be generated

1. CK, GLDH, GGT:

- Changes and percent changes from baseline will be summarized descriptively in tabular format for fordadistrogene movaparvovec and placebo by visit. Observed values will be displayed graphically using box plots for fordadistrogene movaparvovec and placebo by visit.

Changes from baseline for GGT and GLDH will also be summarized using shift tables for fordadistrogene movaparvovec and placebo. The shift table will use baseline values categorized as $>ULN$ -and $\leq 2.5 \times ULN$, >2.5 and $\leq 5.0 \times ULN$, >5.0 and $\leq 20.0 \times ULN$, $>20.0 \times ULN$) for GGT, and $\geq 2 \times ULN$ and $<3 \times ULN$, $\geq 3 \times ULN$ and $<4 \times ULN$, and $\geq 4 \times ULN$ for GLDH, respectively.

2. C3, C4, Platelets, Creatinine:

- Observed values will be summarized descriptively in tabular format for fordadistrogene movaparvovec and placebo by visit.
- Observed values for platelets will also be summarized using shift tables for fordadistrogene movaparvovec and placebo. The shift table will use baseline values categorized as ≥ 75 and $<LLN$, ≥ 50 and <75 , ≥ 25 and <50 , and <25 .
- Observed values will be displayed graphically using box plots for fordadistrogene movaparvovec and placebo by visit.

3. For cTn-I:

For each of the treatments fordadistrogene movaparvovec and placebo, the participants will be divided into two categories: those with baseline cTn-I $\leq 99^{\text{th}}$ percentile (ie. ULN) and those with baseline cTn-I $>99^{\text{th}}$ percentile (ie. ULN). For Centaur assay, the cTn-I 99th percentile (ie. ULN) will be 0.03 ng/ml. The LLoQ is 0.03 and values below LLoQ will set to 0.029. For the Beckman assay, the cTn-I 99th percentile (ie. ULN) will be 19.8 ng/L. The LLoQ is 2.3 ng/L and values below LLoQ will set to 2.29 ng/L. The number and percent of participants in each category by fordadistrogene movaparvovec and placebo will be presented.

For participants at sites where local cTn-I cannot be measured at the Baseline visit, the baseline cTn-I value (last value prior to the IP administration) will be from Screening visit as assessed by the central laboratory.

The observed cTn-I value will be normalized using ULN from the corresponding visit and the ratio of cTn-I/ULN will be summarized descriptively (mean, SD, median, Q1, Q3, minimum and maximum).

Spaghetti plot of the ratio cTn-I/ULN including all participants for each treatment group will be generated. Color pattern will be used for participants with ≥ 2 consecutive visit assessments post-baseline that are $>3xULN$.

All visits (ie, planned and unplanned) will be included in these analyses.

Analysis windows for these summaries and graphical displays by visit are provided in [Appendix 2.1](#).

To assess liver injury, a listing of the participants potentially meeting Hy's Law criteria and E-DISH plots will be produced.

The parameters International normalized ratio (INR), Hepatitis A virus (anti-HAV) immunoglobulin M, Hepatitis B surface antigen, and Hepatitis C antibody will be listed only as they are only collected to assess study entry criteria.

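### Section 6.7.2 pools the cTn-I/ULN ratio over two assays that score an unquantifiable result 0.97 and 0.12, and its cTn-I and GLDH shift grades leave values just above ULN undefined

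*SAP*

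**What the plan says.** SAP Section 6.7.2, item 3, defines the limits for two troponin assays.

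- Centaur: "For Centaur assay, the cTn-I 99th percentile (ie. ULN) will be 0.03 ng/ml", and "The LLoQ is 0.03 and values below LLoQ will set to 0.029".
- Beckman: "For the Beckman assay, the cTn-I 99th percentile (ie. ULN) will be 19.8 ng/L", and "The LLoQ is 2.3 ng/L and values below LLoQ will set to 2.29 ng/L".

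It continues: "The observed cTn-I value will be normalized using ULN from the corresponding visit and the ratio of cTn-I/ULN will be summarized descriptively". A spaghetti plot of the ratio covers all participants in each treatment group. Neither output is split or marked by assay.

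The section also combines central and local laboratory results, and takes a Screening value from the central laboratory as baseline where a site cannot measure cTn-I locally. Table 2 schedules local troponin at Baseline and on Days 2, 4, 6, 8 and 10, and central troponin on Day 7. Appendix 6 records, for SAP version 7, that handling of a new troponin assay was added.

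The table of selected parameters heads its shift-table column with three classes: below LLN, normal and above ULN. The footnotes then list grades. For cTn-I they are "cTn-I/ULN ratio ≥ 3 - <10 , ≥ 10 - <100 , ≥ 100". For GLDH they start at 2xULN (2 to <3, 3 to <4, and 4 or more). For GGT they start just above ULN, and for platelets just below LLN. Item 1 adds: "Changes from baseline for GGT and GLDH will also be summarized using shift tables for fordadistrogene movaparvovec and placebo", with baseline categorised by the listed grades.

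**The concern.** Dividing by ULN is meant to put the two assays on one scale. It cannot do so in the normal range if one assay's quantification limit is its ULN and the other's lies far below it. A visit with more Centaur results would then show a higher typical ratio than a visit with more Beckman results, with no difference in troponin. A boy measured on both assays could show a step in the plot that reflects only the change of assay.

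The shift table raises a second, independent question: where a value modestly above ULN is counted. Section 3.5.2 selects both cTn-I and GLDH for additional analysis, so their displays should be readable without guesswork.

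**Working it through.** The SAP states no derived figure for the ratio, so there is none to reproduce. All inputs are from Section 6.7.2.

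**Score of an unquantifiable result (substitute divided by ULN)**

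- Centaur: 0.029 / 0.03 = 0.967.
- Beckman: 2.29 / 19.8 = 0.116.
- Quotient: 0.967 / 0.116 = 8.4. Difference: 0.967 − 0.116 = 0.85 ULN units.

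**Where the gap comes from**

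LLoQ/ULN is 0.03/0.03 = 1.00 on Centaur and 2.3/19.8 = 0.116 on Beckman. A Centaur result at or below ULN can therefore score only 0.967, or 1.00 if it is exactly 0.03. Beckman can score anything from 0.116 to 1.00. Another substitute does not help: half the LLoQ gives 0.015/0.03 = 0.500 and 1.15/19.8 = 0.058, still 8.6-fold apart.

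**Effect on a visit mean**

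Assume every value at a visit is unquantifiable and a share s was measured on Centaur. The mean ratio is s × 0.967 + (1 − s) × 0.116.

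| s | mean ratio |
|---|---|
| 0 | 0.12 |
| 0.25 | 0.33 |
| 0.50 | 0.54 |
| 0.75 | 0.75 |
| 1 | 0.97 |

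The SAP gives no value for s, so this is the full range under that assumption. For quantifiable Beckman values the gap is smaller. An assumed 10 ng/L scores 10/19.8 = 0.51, and 0.967/0.51 = 1.9.

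**Outputs that do not move**

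Both substitutes give ratios below 1. Neither can carry a result across ULN or 3xULN, so the baseline split at ULN, the grades from 3xULN upwards and the colour flag for >3xULN stand.

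**Coverage of the shift grades**

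- cTn-I at 1.5, 2.5 or 2.99xULN falls in no listed grade; 3xULN is the first that does.
- GLDH at 1.5xULN falls in no listed grade; 2.5xULN falls in the first.

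There are three ways to combine the heading with the lists:

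1. The lists are grades added to normal. GGT and platelets are then contiguous, but cTn-I from >1 to <3xULN and GLDH from >1 to <2xULN have no class.
2. The heading's class above ULN is kept as well. It then overlaps every listed elevated grade, unless it is meant as a remainder class, which the SAP does not say.
3. The lists stand alone. Normal values then have no class either, for GGT as well as for GLDH and cTn-I.

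**The case against.** Much of the case against a stronger reading stands.

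- The artefact lies wholly at or below ULN and touches no categorical or flagged troponin result.
- The eight-fold gap needs a result below LLoQ on both assays. It is the extreme, not the gap for every boy with normal troponin.
- The root is an assay limit, not a poorly chosen substitute. This is why the remedy is to separate the assays rather than impute differently.
- A reader might infer that boys who changed assay will be reported with large percent changes. The SAP does not plan this. The cTn-I table entry is marked as observed values, and item 3 summarises and plots the ratio itself.
- A reader might also infer a bias between arms. Nothing shows that assay use differs by arm. The trial is randomised and double-blind, a change of assay over calendar time would be expected to affect both arms, and the summaries are descriptive.
- A reader might extend the point to liver safety as a whole. That fails. The LLoQ problem does not concern GLDH, which keeps its change and percent-change summaries and box plots. The GGT shift table, the Hy's Law listing and the E-DISH plots also remain.

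On the shift table, it is fair to say that the heading may be intended to supply normal and above-ULN classes. Loss of mildly raised values is therefore not proven. But the SAP does not say how heading and lists combine, and the objection does not resolve that.

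**Conclusion.** The point holds in two limited parts.

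First, the pooled cTn-I/ULN ratio is not comparable across assays at or below ULN. Its by-visit descriptive statistics and its plot depend partly on assay mix, by up to 0.85 ULN units in the extreme case where all values are unquantifiable. The actual size depends on the mix and on the proportion of unquantifiable results, and the SAP gives neither. It also does not say which laboratory used which assay, or whether any boy was measured on both.

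Second, the shift tables leave cTn-I from >1 to <3xULN and GLDH from >1 to <2xULN without a listed grade, under a heading that either omits or overlaps them. This is an undefined category, not a demonstrated loss of data.

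Neither part affects an efficacy analysis. Both make safety displays harder to interpret and are cheap to settle.

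**What to change.** In Section 6.7.2, item 3:

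- Summarise the numeric cTn-I/ULN ratio separately by assay.
- Mark the assay for each point in the spaghetti plot.
- In any display pooled over assays, put all values at or below ULN in one class.

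In the shift-table footnotes and the matching text, replace the heading and partial lists for these two parameters with exhaustive, non-overlapping classes on both axes:

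- cTn-I (xULN): ≤1; >1 to <3; ≥3 to <10; ≥10 to <100; ≥100.
- GLDH: ≤ULN; >ULN to <2xULN; ≥2 to <3xULN; ≥3 to <4xULN; ≥4xULN.

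The cost is SAP wording and table shells, with no new data. The small downside is fewer boys per cell where the ratio is split by assay.
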